## 10 STATISTICAL ANALYSES

### 10.1 General Considerations

Data will be presented using summary statistics. For example, categorical data may be presented as proportions and counts; continuous data may be presented with the mean, median, minimum, maximum, and/or standard deviation.

### 10.2 Analysis Populations

#### 10.2.1 Intent-to-Treat

All subjects who enrolled in the study and underwent study procedure will be included in the intent-to-treat (ITT) population. All safety analyses will be evaluated in the ITT population.

#### 10.2.2 Full Analysis Set (FAS)

All subjects enrolled in the study who have a FWS value at baseline will be included in the FAS. Subjects with missing FWS data at the 3-month visit will be imputed as no change and included in the FAS population. Efficacy outcomes will be evaluated in the FAS.

#### 10.2.3 Per Protocol Set (PPS)

The PPS is the subset of subjects in the FAS without major protocol deviations. Major protocol deviations will be decided and finalized at a data review meeting (DRM) that will be conducted prior to database lock. The efficacy analyses will be repeated on the PP population if there is at least a 10% difference in the number of subjects in the PPS and intent-to-treat (ITT) populations.

### 10.3 Subject Disposition

Subject disposition will be presented by:

- Status of subjects follow-up
- Summary of early withdrawal and reason for early withdrawal

### 10.4 Demographics and Baseline Characteristics

Demographic and baseline characteristics of enrolled subjects will be summarized. The factors will include (but not limited to):

- Age
- Gender
- Ethnicity
- Weight
- Height

### 10.5 Primary Efficacy Endpoint Analyses

The primary efficacy endpoint is the comparison of the proportion of subjects (i.e. percentage of treatment responders) with a  $\geq 1$ -score improvement on the FWS at the 3-month visit, as compared to baseline as determined by at least 2 out of 3 blinded Independent Photographic Reviewers. The study design assumes a 75% success rate of subjects with treated wrinkles with a  $\geq 1$ -score change on the FWS. The percentage

of subjects with a  $\geq 1$ -score improvement will be summarized as counts and percentages. This percentage will be compared to the cutoff of 75% using a binomial exact test (one-sided). Descriptive upper 95% confidence limit will be provided for the difference between treatment and cutoff rate and the associated p-value will also be provided.

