#### 8.4 Sample Size Considerations

The objective of this study is to demonstrate that study participants positively respond to the J-Plasma® therapy, thus the primary endpoint will be assessed via the percentage of study participants that demonstrated an improvement in the FWS from baseline to the 3-month visit. An improvement is clinically important when there is  $\geq 1$ -score change. The planned sample size to provide sufficient power for a statistical comparison of the proportion of treatment responders (P) versus a reasonable cutoff ( $P_0$ ) was based on a power calculation utilizing the (one proportion) binomial exact test based on the following assumptions.

- $H_0: P \leq P_0$  versus  $H_a: P > P_0$
- Type I error rate:  $\alpha = 0.05$  (one-sided)
- Population proportion under the null hypothesis:  $P_0 = 0.75$
- Population proportion under the alternative hypothesis:  $P = 0.90$
- Total N: 50 study participants

Based on the above assumptions, the study power is estimated to be approximately 88%. To account for possible missing data (up to 10% attrition), a total of 55 subjects will be enrolled. Other tests (i.e., a test of the mean improvement of FWS) would be expected to provide more power.

One study investigating the effects of radiofrequency energy on the improvement of appearance of wrinkles and rhytides (De Novo, Newa™) utilized a FWS cutoff as 75%, supporting this value in the present sample size computation.

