### 9.4 Pooling Data Across Sites

Pooling of outcome data from different clinical study sites will be performed by evaluating the homogeneity of the efficacy endpoint across sites, using the Chi-square test statistic. If homogeneity is demonstrated across sites, then the endpoint results will be combined across all clinical study sites.

If significant heterogeneity is observed amongst sites (significant difference in Chi-square test), then the primary endpoint will be additionally presented with a random site adjusted estimate and confidence interval.

Sites with less than five (5) patients enrolled will be combined into a pseudo-site for purposes of analysis. To protect against having an overly large pseudo-site, when one pseudo-site exceeds ten subjects, a second pseudo-site will be formed. This process will continue as needed each time a pseudo-site exceeds ten subjects.

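### The confidence limit planned for the primary endpoint is an upper limit, but the test that the response rate exceeds 75% calls for the lower one; the decision is unaffected

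*SAP*

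**What the plan says.** SAP section 8.4 sets the null hypothesis that the response rate is at most 75% against the alternative that it is higher, at one-sided alpha 0.05. The design assumption is a true rate of 90%. It gives "Total N: 50 study participants" and says that "the study power is estimated to be approximately 88" per cent; enrolment is raised to 55 for attrition.

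Section 10.5 repeats the direction of the test: "This percentage will be compared to the cutoff of 75% using a binomial exact test (one-sided"). It reports counts, percentages and the p-value, and adds: "Descriptive upper 95% confidence limit will be provided for the difference between treatment and cutoff rate".

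The only other interval for the primary endpoint is in section 9.4. If the sites differ significantly, "then the primary endpoint will be additionally presented with a random site adjusted estimate and confidence interval". That interval is conditional and may never be produced.

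**The concern.** A one-sided test that a rate exceeds a cutoff has one matching confidence bound: the lower limit of the rate, or of the rate minus the cutoff. If that limit lies above the cutoff, the test rejects. It also tells the reader how low the true response rate could plausibly be, which is what a claim against a performance goal rests on.

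Section 10.5 names the other side. The phrase puts treatment first, so the natural reading is treatment minus cutoff, and its upper limit says only how large the benefit could be. If the authors meant cutoff minus treatment, the upper limit would be correct, but the SAP does not say so. The sentence therefore gives either the wrong bound or a bound of undefined sign, and a programmer could implement either.

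At stake is the reporting of the main result. Section 8.1 expects the 510(k) application to be submitted on the 3-month results. As written, the one bound always shown beside the primary result would say nothing useful on whether the rate exceeds 75%.

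**Working it through.** **Inputs.** From section 8.4: cutoff P0 = 0.75, alternative P = 0.90, one-sided alpha 0.05, N = 50 for power and 55 enrolled. Both sizes are used because sections 9.2 and 10.2.2 count subjects with a missing 3-month score as unchanged, so the analysed number can be as high as 55.

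**Step 1: reproduce the stated power.** The exact test rejects at the smallest count r for which P(X ≥ r | N, 0.75) ≤ 0.05. For N = 50:

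- P(X ≥ 42 | 50, 0.75) = 0.0916, so 42 fails.
- P(X ≥ 43 | 50, 0.75) = 0.0453, so r = 43.
- Power = P(X ≥ 43 | 50, 0.90) = 0.878, which agrees with the stated 88%.

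At one-sided 0.025, r would be 44 and power 77.0%. The stated power therefore belongs to the one-sided 0.05 test in the upper tail.

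**Step 2: the limits.** For x responders among n, the exact (Clopper-Pearson) one-sided 95% limits are:

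- Lower limit L solves P(X ≥ x | n, L) = 0.05, so L is the 0.05 quantile of Beta(x, n − x + 1).
- Upper limit U solves P(X ≤ x | n, U) = 0.05, so U is the 0.95 quantile of Beta(x + 1, n − x).

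Subtract 75% from each to get the difference. By construction, L exceeds 75% when the exact p-value P(X ≥ x | n, 0.75) is below 0.05.

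**Step 3: results (rate minus 75%, in percentage points).**

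| Responders | Rate | One-sided p | Lower limit | Upper limit |
|---|---|---|---|---|
| 35/55 | 63.6% | 0.979 | -23.3 | -0.6 |
| 36/55 | 65.5% | 0.960 | -21.5 | +1.1 |
| 46/55 | 83.6% | 0.089 | -1.8 | +16.2 |
| 47/55 | 85.5% | 0.045 | +0.3 | +17.6 |
| 31/50 | 62.0% | 0.986 | -25.6 | -1.5 |
| 32/50 | 64.0% | 0.971 | -23.6 | +0.3 |
| 42/50 | 84.0% | 0.092 | -2.0 | +16.8 |
| 43/50 | 86.0% | 0.045 | +0.3 | +18.2 |

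At both sizes the lower limit changes sign at the count where the test becomes significant. The upper limit is positive for every success, and also for all failing results from 36 to 46 of 55, or from 32 to 42 of 50.

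**Step 4: how often a failing trial would show a positive upper limit.** For N = 55 this is P(36 ≤ X ≤ 46) / P(X ≤ 46).

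- True rate 0.75: (0.9546 − 0.0405) / 0.9546 = 0.958.
- True rate 0.70: (0.9934 − 0.1875) / 0.9934 = 0.811.

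**Step 5: the reversed difference.** For cutoff minus treatment, the upper limit is 75% − L. It is +1.8 points at 46/55 and −0.3 at 47/55, so it would change sign with the test. The order of subtraction thus decides whether the sentence is right.

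**Step 6: sensitivity to the type of limit.** Section 10.5 names no interval method and does not say whether the limit is one-sided. As the upper end of a two-sided 95% exact interval, it would turn positive one responder earlier: 35/55 (+1.2 points) and 31/50 (+0.35). The conclusion is the same.

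**The case against.** The strongest reply is that nothing inferential depends on this sentence. The exact test decides, its p-value is reported, and the limit is labelled descriptive. No section makes it a success criterion. That stands: alpha, power, sample size and pass or fail are untouched. The percentages in step 4 describe how little the bound says about the hypothesis; they are not a rate of wrong decisions, because each failing trial would also report a non-significant p-value.

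Second, the counts are reported, so anyone can compute the lower limit. This is also true. But the p-value does not give the size of the margin, and a prespecified primary analysis should not leave that to the reader. Sections 10.8 and 10.9 plan 95% confidence intervals of the mean for several lesser endpoints.

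Third, the upper limit is not empty: it bounds how large the benefit could be, and at 35/55 or fewer it would show a rate below the cutoff. This is a fair qualification. It is uninformative only about whether the rate exceeds 75%.

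Fourth, cutoff minus treatment may have been intended. Step 5 shows that this would rescue the sentence, but the SAP does not state it, so the text needs an edit either way.

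**Conclusion.** The concern holds. On its natural reading, section 10.5 plans the wrong side of the interval; on the other reading, it leaves the sign undefined. It is the only unconditional bound planned for the primary endpoint, and it is positive from about 65% responders upward, whereas success needs 47/55 or 43/50.

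The size is limited: this is a reporting error with no effect on the test, its error rate or its power. It should be fixed because the correction is nearly free, but it ranks low in severity. The exact counts quoted assume one-sided 95% Clopper-Pearson limits and an analysed number of 50 or 55. The mismatch of direction does not depend on those choices.

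**What to change.** Replace the sentence on the confidence limit in section 10.5 with wording such as:

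> *The exact (Clopper-Pearson) one-sided lower 95% confidence limit will be given for the response rate and for the response rate minus 75%, together with the one-sided exact binomial p-value. A lower limit above 75% (a difference above 0) corresponds to rejection of the null hypothesis at one-sided 0.05.*

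A two-sided 90% exact interval has the same lower end and would also show the upper side. A two-sided 95% interval would not match the test at the boundary: at 43/50 its lower end is 1.7 points below the cutoff although p = 0.045.

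The cost is one sentence in the SAP and one option in the program. Sample size, test and decision rule stay as they are.

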## **10.6 Secondary Efficacy Endpoint Analyses**

Subjects with a  $\geq 1$ -score improvement on the FWS and at least a self-reported “improved” rating on the modified GAIS at the 3-month visit will be considered to have an aesthetic pleasing outcome. An “improvement” on the modified GAIS by the treating investigator at the 3-month visit will be classified as “improved,” “much improved,” or “very much improved.” All other ratings on the modified GAIS will be classified as “no improvement.” Cross-tabulation of improvement status of modified GAIS versus 1-score FWS response will then be summarized as counts and percentages.

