### 7.3 Secondary Efficacy Endpoint

Subjects with a  $\geq 1$ -score improvement on the FWS and at least a self-reported “improved” rating on the modified GAIS at the 3-month visit will be considered to have an aesthetic pleasing outcome. The modified GAIS is a measure of aesthetic improvement relative to the baseline, pre-treatment condition.

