**Table 1. Study Required Procedures**

	Baseline/ Pre- Procedure Screening 	Procedure	10 Days	1 mo	3 mo	6 mo
			10+4/-1 days	30±7 days	90±10 days	180±14 days
Informed Consent	✓					
Assess Inclusion/Exclusion Criteria	✓					
Urine Pregnancy Test 	✓	✓				
Medical History	✓					
General Physical Exam	✓					
Review Medications	✓		✓	✓	✓	✓
Photographic Images 	✓		✓	✓	✓	✓
Fitzpatrick Skin Scale (FSS)	✓					
Fitzpatrick Wrinkle and Elastosis Scale (FWS) 	✓		✓	✓	✓	✓
Visual Analog Scale (10-point VAS) 		✓	✓	✓	✓	✓
Study Procedure		✓				
Subject Diary (10-point VAS) 		✓	✓			
Adverse Event Assessment		✓	✓	✓	✓	✓
Re-epithelialization and Down Time 			✓	✓	✓	
Modified Global Aesthetic Improvement Scale (GAIS) 			✓	✓	✓	✓

 Pre-procedure Screening assessments to take place within 21 days prior to undergoing the procedure.  
 Up to two urine pregnancy tests must be obtained prior to study procedure for females with child-bearing potential (one at pre-procedure screening and one on the day of the procedure prior to the procedure if screening and procedure are not performed on the same day).  
 Digital photographs of the subject's face will be taken and labeled according to Photography Instructions.  
 To be completed by Investigator and Independent Photographic Reviewers (IPRs).  
 To be completed by the study subject on a day of the procedure (prior to the procedure and immediately following the procedure) and at all follow-up visits.  
 To be completed by the study subject daily starting from the day of procedure (after procedure, at home) until the 10 day follow-up visit.  
 To be completed by Investigator and/or Independent Photographic Reviewer (as applicable) to capture achievement of epidermal recovery status at follow-up visits; and date when study subject felt comfortable, willing and able to go in public following study procedure (assessed at the 10 day follow-up visit).  
 To be completed by Investigator and study subject at all study follow-up visits.

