### 9.2 Missing Data

If applicable, a list of subjects who were withdrawn/lost to follow-up from the study and associated reasons will be provided.

Subjects with missing 3-month FWS data will be imputed as having no change from baseline. No other imputations for missing data will be employed. Furthermore, no estimation of missing data for self-reported pain within the 10 day Subject Diary will be imputed.

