## **10.9 Additional Analyses**

Other endpoints to be evaluated include:

**10.9.1** FWS  $\geq 1$ -score improvement and  $\geq 75\%$  agreement with at least an “improved” rating by the subject on the modified GAIS. An “improvement” on the modified GAIS by the subject at the 3-month visit will be classified as “improved,” “much improved,” or “very much improved.” All other ratings on the modified GAIS will be classified as “no improvement.” Cross-tabulation of improvement status of modified GAIS versus 1-score FWS response will then be summarized as counts and percentages.

**10.9.1.1** Magnitude of improvement measured by the mean change in FWS from baseline to 3-month visit. Descriptive summary statistics (number of observations, mean, standard deviation, minimum, maximum, median, 95% confidence interval of the mean) will be used for summarizing the change in FWS from baseline to the 3-month visit. The FWS from baseline to the 3-month visit will also be stratified on both the treating-investigator and subject modified GAIS.

**10.9.1.2** Subject satisfaction with procedure recorded at the 3-month visit. Results of VAS on a scale of 0 to 10 will be summarized descriptively utilizing mean, standard deviation, minimum, maximum, median, and the 95% confidence interval of the mean. Cross tabulation of subject satisfaction/improvement versus 1-score FWS response will be summarized as counts and percentages.

**10.9.1.3** Achievement of re-epithelialization by facial zone (and across facial zones) at the 10-day, 1-month and 3-month follow-up visits as reported by the study investigator and/or Independent

Photographic Reviewers (as applicable). Descriptive summary statistics (number of observations, mean, standard deviation, minimum, maximum, median, 95% confidence interval of the mean) will be used for summarizing the achievement of re-epithelialization by facial zone and across facial zones at all follow-up visits through the 3-month visit.

**10.9.1.4** Mean duration (days) until subject feels comfortable going in public after treatment as reported the study subject. Descriptive summary statistics (number of observations, mean, standard deviation, minimum, maximum, median, 95% confidence interval of the mean) will be used for summarizing the mean duration for study subject to feel comfortable after treatment.

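### SAP 10.6 classifies the modified GAIS by the treating investigator's rating, although the secondary efficacy endpoint is defined by the subject's own rating

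*SAP*

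**What the plan says.** SAP 7.3 names one secondary efficacy endpoint, the aesthetic pleasing outcome at 3 months. It has two components, an FWS response and a favourable GAIS rating given by the subject: "improvement on the FWS and at least a self-reported". The first sentence of 10.6 repeats this definition.

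The second sentence of 10.6 says when a GAIS rating counts as improvement. It applies to a rating "on the modified GAIS by the treating investigator at the 3-month visit will be classified as" one of the three favourable categories, and every other rating counts as no improvement. The section then ends with its only output: "Cross-tabulation of improvement status of modified GAIS versus 1-score FWS response will then be summarized as counts and percentages".

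Three other places bear on this:

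- Table 1, footnote 8, on the GAIS: "To be completed by Investigator and study subject at all study follow-up visits".
- Section 10.9.1, for an additional endpoint that also carries a 75% agreement criterion, uses the same classification rule with the other rater: "on the modified GAIS by the subject at the 3-month visit will be classified as". It plans the same kind of cross-tabulation.
- Section 10.9.1.1 says that the FWS result "will also be stratified on both the treating-investigator and subject modified GAIS".

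**The concern.** The endpoint is defined by one rater and its analysis rule by another. A programmer building the 10.6 table would take the investigator's GAIS variable, because that is the only improvement status the section defines. The table labelled as the secondary efficacy result would then show how many FWS responders the treating investigator judged improved. The endpoint asks how many considered themselves improved.

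The subject-rated table would appear only among the additional analyses, under a different endpoint label. A reader would have two similar tables, with the one under the secondary heading not matching its definition. Section 8.1 expects the 510(k) submission to rest on the 3-month results, which is the time point of this endpoint.

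**Working it through.** The SAP gives no figure for this endpoint: no test, threshold or expected rate. Its one design figure, the power of about 88% in 8.4, belongs to the primary endpoint. That figure reproduces: with N = 50, the exact one-sided test rejects at 43 or more responders (alpha 0.0453 at P0 = 0.75, power 0.878 at P = 0.90). It does not depend on the GAIS. The check is therefore mainly a comparison of text.

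**Step 1. Which rater does each place name?**

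| Place in SAP | Function | GAIS rater |
|---|---|---|
| 7.3 | Defines secondary endpoint | Subject |
| 10.6, first sentence | Repeats definition | Subject |
| 10.6, second sentence | Classifies improvement | Treating investigator |
| 10.6, last sentence | Cross-tabulates with FWS response | Not named; follows from the rule before it |
| 10.9.1 | Classifies improvement for an additional endpoint | Subject |
| 10.9.1.1 | Stratifies FWS result | Both, as separate variables |
| Table 1, footnote 8 | Data collection | Both |

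Section 10.6 conflicts with 7.3 and with its own first sentence. Footnote 8 and 10.9.1.1 exclude the reading that there is only one GAIS rating.

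**Step 2. What does the difference amount to?** Among FWS responders, let *a* be the number rated improved by both raters, *b* by the investigator only, and *c* by the subject only. Take N = 55, the planned enrolment, assuming every enrolled subject has a baseline FWS and so enters the FAS.

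- Endpoint as defined in 7.3: (a + c)/55
- Joint cell of the 10.6 table as written: (a + b)/55
- Difference: (a + b)/55 − (a + c)/55 = (b − c)/55

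Each discordant responder contributes 1/55 = 0.0182, or 1.8 percentage points. Discordances in opposite directions cancel. The SAP gives neither *b* nor *c*, so the size and sign of the net difference are unknown.

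**Step 3. Who is in the denominator?** Section 10.2.2 says "Efficacy outcomes will be evaluated in the FAS", and 9.2 says "Subjects with missing 3-month FWS data will be imputed as having no change from baseline". A subject without a 3-month FWS is therefore a non-responder, fails the composite whatever the GAIS shows, and stays in the denominator. The only undetermined case is an FWS responder with no GAIS rating, because 9.2 permits no other imputation.

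**Step 4. Is the right quantity available elsewhere?** Yes. The cell of the 10.9.1 table for FWS responders whom the subject rated improved or better counts a + c, the numerator of the 7.3 endpoint.

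**The case against.** The strongest counter-argument is that the slip may lie in the other direction. If the secondary endpoint is subject-rated, it nearly duplicates the additional endpoint in 7.5 item 1 and 10.9.1, apart from the agreement criterion. If it was meant to be investigator-rated, 10.6 and 10.9.1 form a natural pair, one for each rater. This has some force, and the protocol that could settle it is not at hand. However, the SAP states the endpoint definition twice, both times as self-reported, and nowhere defines the composite by the investigator's rating. Even on the alternative reading, 7.3 and 10.6 would still have to be reconciled.

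A second argument is that the last sentence of 10.6 names no rater, so the table could be built from the subject's rating. That is possible but not the natural reading, since the table follows directly from the investigator-based rule. If the sentence is read as open, the section is ambiguous on a named endpoint and needs the same edit.

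Third, the information is already planned in 10.9.1 and nothing inferential depends on it. This is correct and limits the weight of the point. The 1.8-point figure also depends on the denominator: a table restricted to about 50 subjects with data would give 1/50 = 2.0 points each.

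**Conclusion.** The point holds. As written, the rule in 10.6 produces a table for a different rater from the one in the endpoint definition, so it does not report the stated secondary efficacy endpoint. The consequence is a descriptive result that may be off by (b − c)/55, at 1.8 percentage points per discordant FWS responder, with net size and direction unknown. This assumes all 55 planned subjects are in the FAS.

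Alpha, power, sample size and the primary conclusion are unaffected, and the correct count can be recovered from 10.9.1. The correction should be made, though nothing in the trial's main inference turns on it.

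**What to change.** 1. In the classification sentence of 10.6, replace the treating investigator with the subject as the GAIS rater, so that it agrees with 7.3. Check this against the protocol. If the protocol defines the endpoint by the investigator's rating, 7.3 and the first sentence of 10.6 are the texts to change.
2. Add to 10.6 that the number and proportion of FAS subjects meeting both criteria will be reported, in addition to the cross-tabulation. Subjects with a missing 3-month FWS already count as failures under 9.2 and 10.2.2, so no GAIS imputation is needed for them.
3. If an FWS responder with a missing GAIS is also to count as a failure, say so in 9.2. This is optional.
4. Move the investigator-rated cross-tabulation to 10.9 as a supportive analysis. Let 10.9.1 refer to 10.6 for the subject-rated table, keeping its own endpoint and the 75% agreement criterion.

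The cost is SAP wording in 10.6 and 10.9, plus 9.2 if item 3 is adopted. Both ratings are already collected at 3 months, so no new data are needed and no planned table is lost.
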